VALIDATION OF A SEVERITY SCORE TO IDENTIFY PATIENTS ADMITTED FOR COVID-19 PNEUMONIA AT HIGH RISK FOR AN INTENSIVE APPROACH

Versione del 17 aprile 2020

[name], [name], [name], [name], [name], [name], [name], [name], [name], Unità di Ricerca Covid, Fondazione Policlinico Gemelli, IRCCS, Catholic University Rome, Italy

INTRODUCTION

The outbreak of the coronavirus disease 2019 (COVID-19), first merged in China in December 2019, is now becoming a Public Health Emergency, recently confirmed as a pandemic disease by the World Health Organization (WHO) (1). It has been estimated that the worldwide number of confirmed cases nearly amount to 1 million with more than 40000 deaths (1).

In particular, since February 2020, a rapidly growing number of cases has been identified in Italy; current data reveal a number of infected over 110000 subjects, with more than 13000 deaths and 4000 hospitalization in intensive care units (2).

The clinical picture of ranges from asymptomatic cases, mild upper respiratory tract infections to severe pneumonia with respiratory failure and death (3). In most severe cases, COVID-19 disease may be complicated by acute respiratory distress syndrome (ARDS), septic shock and multiorgan failure (4).

Since now, more than 30 agents have been tested for efficacy against SARS-CoV-2 and safety, with promising but still not conclusive evidences (5).

Therefore, it results fundamental to early identify those subjects who rapidly may worsen their clinical status, often requiring an intensive care unit (ICU) admission.

It has been showed that, mainly in more severe forms of SARS-Cov-2 disease, there is the development of an hyperinflammatory status resembling a cytokine storm syndrome (6), as already reported in SARS patients (7).

A recent study by Haung et al. reported that patients with COVID-19 infection showed high amounts of IL1B, IFN-gamma, IP10 and MCP1, probably linked to activated T-helper1 (Th1) cell responses.

Those requiring ICU admission had higher levels of cytokines than those subjects not requiring ICU admission, thus suggesting that cytokine storm was associated with disease severity (6).

A similarity between cytokine profile of COVID-19 disease and secondary haemophagocytic syndrome (sHLH) has been reported (4). Therefore, it was suggested to screen all patients with severe COVID-19 infection both for hyperinflammatory markers (like ferritin), and the HScore commonly used to generate a probability for diagnosis of sHLH (8), which includes some laboratory parameters like triglycerides, fibrinogen, ferritin, serum aspartate aminostransferase (8).

A recent retrospective analysis on 487 COVID-19 Chinese patients admitted to Hospital, showed that the 49 (10.1%) severe cases at admission, was elderly, more commonly male and had a higher incidence of hypertension. Therefore, the Authors defined a host risk score on the basis of the three risk factors, aimed to assess the intrinsic host susceptibility to develop severe cases of COVID-19. This score was also validated in 15 out of 66 patients with a mild to moderate presentation of disease at admission, who showed a progression of disease during hospital stay within a median follow-up time of 15 days (9).

Another work by Zhou et al. on 191 Chinese COVID-19 patients showed that older age, D-dimer levels greater than 1 μ g/mL, and higher SOFA score on admission were associated with higher odds of in-hospital death (10). Moreover, subjects with most severe forms of COVID-19 illness commonly showed high levels of blood IL-6, high-sensitivity cardiac troponin I, lactate dehydrogenase and lymphopenia (10).

Based on our previous experience with a large number of patients affected by pneumonia from Covid19, we have observed that those subjects with a more severe prognosis might have some predictive markers. We intend to verify if these markers can identify those subjects with Covid19 infection who need a more intensive therapy and to find a prognosis score.

Methods

Before starting the study, the protocol will be submitted to and approved by the local Ethical Committees at the Fondazione Policlinico Universitario A. Gemelli IRCCS, Catholic University, Rome, Italy. Before enrollment each subject will sign the informed consent.

Inclusion criteria: subjects of both sexes aged 18 years or older consecutively hospitalized with diagnosis of pneumonia, confirmed by chest imaging, Covid-19 test positive, given informed consent to data collection from the patient.

Exclusion criteria: age lower than 18 years, pregnancy or breast-feeding.

Nasopharyngeal swab samples will be taken for quantitative real-time polymerase chain reaction to make diagnosis of Covid19 (2 repeated tests).

Data collected include time of type of symptoms (cough, fever, dyspnea, conjunctivitis, diarrhea, asthenia, arthralgia) and duration, comorbidities (presence of diabetes, hypertension, cardiovascular disease), PaO2/FiO2 ratio, age, sex, height, weight, triglycerides, complete blood count, D-dimer, lactic acid dehydrogenase (LDH), high-sensitivity C-reactive protein (hs-CRP), albumin, and ferritin. The duration of the follow-up will be 28 days from the patient's hospitalization or until his/her discharge or death.

Primary end-point

The primary end-point is to identify the best predictors of critical coronavirus pneumonia and to realize a simple severity score able to early classify high-risk individuals admitted to Internal Medicine Department for COVID-19 disease, needing an intensive approach.

The evaluated predictors for the score assessment are the following: symptoms duration, type of symptoms (cough, fever and dyspnea), comorbidities (presence of diabetes, hypertension, ischemic heart disease), PaO2/FiO2 ratio, age, sex, body mass index (BMI), triglycerides, white cell count, lymphocyte count, D-dimer, lactic acid dehydrogenase (LDH), high-sensitivity C-reactive protein (hs-CRP), albumin, and ferritin. These parameters were collected at admission.

Sample size calculation

The sample size determination is based on the following considerations:

1) the objective of the study is that of finding the best predictors of severe coronavirus pneumonia outcome;

 the study sample will be constituted by inpatients cases of COVID-19 admitted to Internal Medicine Department of Fondazione Policlinico A. Gemelli IRCCS;

3) in order to test the predictive ability of the developed score the study sample will be split into a fitting population and a validation population by using the internal/validation/data-splitting method 4) the following rule-of-thumb will be considered: the power for a test of a medium-sized partial correlation between y and a predictor, holding all other predictors constant, is approximately .80 if N = 104 + m, where m is the number of predictors (11).

Starting from the above considerations, and from the hypothesis that about 20 predictors will be evaluated for development of a risk score able to predict the severe coronavirus pneumonia outcome, the population size of the fitting population is set to N = 104+20=124 patients. In the procedure of splitting the data set into a fitting population and a validation population, the 50% of the entire sample will be used for the fitting step and the remaining 50% will be used as a validation population. A sample size of 248 patients will be therefore necessary.

Statistical Analysis

Primary Analysis

The data set will be split into a fitting population and a validation population by using the internal/validation/data-splitting method. The internal/validation/data-splitting method is chosen to limit the possible increase in bias that can occur with other techniques for internal validation such as

Bootstrapping technique if the original study population contains biases. The portion of the population used as fitting population for model development will be chosen randomly. The model will be then tested, in terms of its performance on the remaining validation population. Computation of the C statistic will be used to indicate the discrimination performance of the model. The C statistic represents a measure of the model's performance in terms of the model discrimination ability to separate subjects with different outcomes, and for the logistic model, it is equivalent to the area under the curve of the receiver operating characteristic (ROC) curve associated to the model (12) Values of C between 0.8 and 0.9 will be considered to give an excellent discrimination.

Computation of the probabilities: For each subject, both from the fitting population and the validation population, the probability of the studied outcome will be computed on the basis of the patient's covariate values. Each subject will be therefore characterized by the values of the covariate set, the outcome (coronavirus-severity, 0/1) and by the estimated probability of the outcome.

Computation of the C statistics: For both the fitting and the validation populations, the C statistics will be computed. The accuracy (percentage of true positive and negative on the total subjects) of the prediction model will be also computed.

Procedure repetition: The entire procedure (data splitting, model fitting, probability computation) will be repeated 200 times.

Model fitting onto the whole population: The model will then be fitted using all the original data.

Results analysis: At the end of the procedure, the distribution of different indicators will be computed: for each variable, frequency histograms of the estimated coefficients along with their associated standard errors and levels of significance will be plotted. The importance index of each variable computed from each data splitting and model fitting will be also plotted.

The estimated coefficients from the whole population will be compared with the respective distributions (they should be centred around the estimates obtained on the whole sample); the distribution of the variability of the model coefficients indicates to which extent the results are dependent from the subpopulation used; comparison between the distribution of the C statistic computed on the fitting and the validation sample, along with the distribution of their Delta provide indication of the discrimination power of the model. It is expected that the C statistic is larger for the fitting sample than for the validation sample. A model with a high discrimination power presents small drops in the values of the C statistic when computed on the validation sample with respect to

values computed on the fitting sample for which the values are expected to be larger (C Delta distribution centred around the zero).

On the basis of the obtained results on the full model, the entire procedure is repeated on the subset of the most important variables to test and validate the final reduced model including the most meaningful predictors. Once the model validation is assessed the fitted coefficients used to compute the probability of the outcome on a generic patient will be those obtained from the "reduced model" fitting on the whole population sample.

Secondary analyses

Secondary analyses include the use of other classification procedures to compare results from the primary analysis. One of the classification procedures that will be used to classify patients with severe and non-severe coronavirus pneumonia outcome, on the basis of the collected variables, will be the Partial Least-Squares Discriminant *Analysis (PLS-DA)*. A cross validation approach will be followed and the optimal model with the optimal number of PLS components will be derived. The Q2 value, the ROC AUC and the derived misclassification error, by the classification Youden criterium, will be used to quantify the classification goodness. A permutation approach, including 1000 random permutations, will be used in order to associate a P level to the obtained Q2 value. Random forest classification procedure, which is based on learning algorithms, will be also tested following the same procedure of splitting the entire sample into a training set and a test set. Univariate analyses studying the association between severity and predictors will be conducting using Chi-Squared tests or Fisher exact tests when appropriate or univariate logistic regression models for quantitative variables. Secondary analyses will have only an explorative purpose.

REFERENCES

5) Dong L et al. Discovering drugs to treat Coronavirs Disease 2019 (COVID-19). Drug Discov Ther 2020

7)Womg CK, et al. Plasma inflammatory cytokines and chemokines in severe acute respiraoty syndrome. Clin Exp Immunol 2004;

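### The primary end-point asks for a score that classifies high-risk patients, but the primary analysis sets no cut-off and tests only C and overall accuracy, which can look high while many severe patients are missed

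*Combined protocol and SAP*

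**What the plan says.** The section on the primary end-point sets the aim: "to realize a simple severity score able to early classify high-risk individuals". The sample size section gives the reason for splitting the data: "in order to test the predictive ability of the developed score the study sample will be split".

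The primary analysis computes an outcome probability for each patient, then C in both halves, and adds a second measure: "The accuracy (percentage of true positive and negative on the total subjects". No probability cut-off accompanies it. The procedure is repeated over 200 random splits.

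Under the results analysis, the plan describes the spread of the coefficients, the importance indices and the difference in C between halves. It then repeats the procedure on the most important variables. The final product is "the fitted coefficients used to compute the probability of the outcome on a generic patient", taken from the reduced model fitted to the whole sample.

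The only cut-off rule in the document is the Youden criterion. It appears under the secondary analyses, for the PLS-DA misclassification error, and those analyses are declared exploratory. Sensitivity, specificity and predictive values are not planned anywhere.

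**The concern.** Classifying patients takes a model and a cut-off. The plan supplies the model only. C measures how well patients are ranked. It does not say how many severe patients a given rule would catch, or how many patients would be flagged unnecessarily.

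Accuracy is the one classification measure in the primary analysis, and it has two weaknesses. It cannot be computed from probabilities without a cut-off, so as written it is undefined. It also weights severe and non-severe patients by their numbers, so when severe outcomes are uncommon it is driven mainly by the non-severe.

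The study could therefore report a C in the range it calls excellent and a high accuracy, and still leave open whether the tool identifies the patients it is meant to identify.

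**Working it through.** **The plan's own figure.** The rule is that power "is approximately .80 if N = 104 + m, where m is the number of predictors". With about 20 predictors, 104 + 20 = 124 for the fitting half. With a 50/50 split, 124 / 0.50 = 248. Both stated figures reproduce, and nothing below changes them.

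**Inputs.**
- C: 0.80 to 0.90, the band that the primary analysis calls excellent.
- Event rate p: not stated in the documents. Two background figures from the introduction serve as illustrations: 10.1% (severe at admission in another cohort) and 15/66 = 22.7% (later progression among initially mild to moderate patients in the same study). Neither is this study's expected rate. 30% and 40% are added to show the range.
- Cut-off t: not stated. 0.5 is assumed first, then the Youden cut-off.
- Model: equal-variance binormal with calibrated probabilities (assumed).

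**Formulas.** Separation d = √2 × z(C). A probability cut-off t corresponds to the marker value c = [logit(t) − logit(p) + d²/2] / d. Then:
- sensitivity = 1 − Φ(c − d)
- specificity = Φ(c)
- accuracy = p × sensitivity + (1 − p) × specificity
- accuracy when nobody is called high risk = 1 − p

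**One case in full: p = 0.101, C = 0.80, t = 0.5.** d = 1.190. c = (0 + 2.186 + 0.708) / 1.190 = 2.432. Sensitivity = 1 − Φ(1.242) = 0.107. Specificity = Φ(2.432) = 0.992. Accuracy = 0.101 × 0.107 + 0.899 × 0.992 = 0.903. A validation half of 124 would hold about 12.5 severe patients, of whom about 11.2 would be missed.

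**Range at t = 0.5.**

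| Event rate | C | Accuracy | Sensitivity | Accuracy, nobody high risk |
|---|---|---|---|---|
| 10.1% | 0.80 | 90.3% | 10.7% | 89.9% |
| 10.1% | 0.90 | 92.2% | 38.2% | 89.9% |
| 22.7% | 0.80 | 80.8% | 33.2% | 77.3% |
| 22.7% | 0.90 | 86.3% | 59.1% | 77.3% |
| 30% | 0.80 | 76.9% | 45.4% | 70% |
| 30% | 0.85 | 80.2% | 56.2% | 70% |
| 40% | 0.80 | 73.5% | 60.0% | 60% |

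Sensitivity at t = 0.5 falls below one half only when p < 1 / (1 + exp(d²/2)). That is about 33% for C 0.80, 25% for C 0.85 and 16% for C 0.90.

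**Youden cut-off.** In this model sensitivity and specificity both equal Φ(d/2), whatever the event rate: 72% at C 0.80, 77% at C 0.85 and 82% at C 0.90. At C 0.80 the positive predictive value is 23% for 10.1% events and 44% for 22.7%.

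**What a validation half can show.** With 10.1% events, 124 × 0.101 is about 13 events, and 10 of 13 detected has an exact 95% CI of 46% to 95%. With 22.7%, about 28 events, 22 of 28 detected has a CI of 59% to 92%.

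**The case against.** Three stronger readings are tempting, and the documents do not support them.

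1. A reader might infer that no score is ever built. The results analysis puts a reduced model through the same splitting and fixes its coefficients, and the document itself uses the word score for a tool that yields a probability. The reduced equation can fairly be called the score. Nothing promises integer points, so requiring them would be a preference.

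2. A reader might infer that accuracy will look high while most high-risk patients are missed. That depends on the cut-off, the event rate and C. At 22.7% events and C 0.90, or 30% and C 0.85, more than half are caught even at 0.5. Under the only cut-off rule the document names, sensitivity is at least 72% for C of 0.80 or more.

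3. A reader might infer that a cut-off will be chosen afterwards on all 248 patients. The plan does not say so. Accuracy is listed alongside C for both halves, so some cut-off has to be applied there. It is unspecified, which is not the same as shown to be post hoc.

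It is also fair to say that C, as the area under the ROC curve, summarises the trade-off between sensitivity and specificity over all cut-offs.

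What these arguments leave standing is narrower. The end-point asks for classification, no cut-off is given, and no operating characteristic of a classification rule is tested. The difference in C and the coefficient stability are examined, but neither tests classification. The Youden-based error belongs to a different, exploratory model.

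**Conclusion.** The point holds in this form: the primary end-point is a score that classifies, but the primary analysis validates a probability equation by C and by an accuracy whose cut-off is undefined. Sensitivity, specificity and predictive values are absent.

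The size cannot be fixed from the documents, because they give neither an event rate nor a cut-off. Under the assumptions above, the same model with C 0.80 at 10.1% events would catch about 1 in 10 severe patients at a 0.5 cut-off and about 7 in 10 at the Youden cut-off. Accuracy would be 90% in the first case and 72% in the second, so judged by accuracy alone the rule that misses more severe patients would look better. At higher event rates or higher C the gap narrows.

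This is a gap in what is specified and reported. It does not invalidate the design, and it is inexpensive to close.

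**What to change.** In each of the 200 splits, use the fitting half only to select the reduced variables, fit the model and choose one probability cut-off by a prespecified rule, for example the Youden criterion already named in the secondary analyses. Apply the model and cut-off unchanged to the validation half. Variable selection has to sit inside the loop. As planned, the reduced set is chosen from results over all the splits, so every patient has already influenced it before the second round of validation.

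Report sensitivity, specificity and predictive values with their spread across splits, alongside C, in place of accuracy as the headline classification measure. Release the equation and cut-off built by the same steps on all patients, and state that the splits estimate the performance of that procedure. A points version is optional. If one is to be released, build and test it in the same loop.

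The cost is some programming and revised wording in the analysis section, with no change to the 248 patients. The estimates will probably be less favourable, and they will be imprecise, as the interval of 46% to 95% for 10 of 13 events shows. With so few events in a fitting half, the chosen cut-off may also vary noticeably between splits, and that variation should be shown.

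### The power of about .80 at 124 patients comes from a linear-outcome rule with no event rate; for the plan's 0/1 outcome it depends on a severe-case rate the plan never states

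*Combined protocol and SAP*

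**What the plan says.** Sample size calculation, point 4, rests on a published rule of thumb for regression: "the power for a test of a medium-sized partial correlation between y and a predictor, holding all other predictors constant, is approximately .80" if N is 104 plus the number of predictors. With about 20 predictors, "the population size of the fitting population is set to N = 104+20=124 patients". A 50/50 split doubles this to 248.

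Under Primary Analysis each subject carries "the outcome (coronavirus-severity, 0/1) and by the estimated probability of the outcome". The model is identified through the C statistic: "for the logistic model, it is equivalent to the area under the curve" of the ROC curve. The outcome is therefore binary and the model logistic.

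The full model is fitted to 200 random halves and then to everyone. Results analysis says that "for each variable, frequency histograms of the estimated coefficients along with their associated standard errors and levels of significance will be plotted". Of these coefficient distributions it says "they should be centred around the estimates obtained on the whole sample". Selection follows: "On the basis of the obtained results on the full model, the entire procedure is repeated on the subset of the most important variables".

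The sample-size text gives no expected rate or number of severe cases, no numerical value for a medium effect, and no significance level. The Introduction reports two rates from one cited cohort: 49 of 487 (10.1%) severe at admission, and 15 of 66 patients with milder disease at admission who progressed in hospital. Neither is offered as a planning assumption.

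**The concern.** The rule concerns a partial correlation in a linear model, where precision depends on N and the number of predictors. In a logistic model with 20 predictors it also depends on how many patients have the outcome. The same 124 patients may hold 28 severe cases or 12, and the rule cannot tell these apart. It is nevertheless the only justification for 124, and so for 248.

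Two things are at stake. One is whether the stated power can be relied on. The other is how the 200 half-sample fits of the full model will behave, since their coefficients, standard errors and significance levels inform the choice of the reduced model. Few events per predictor inflate ordinary maximum-likelihood logistic coefficients, and in the extreme leave no finite estimate. The plan does not say how such splits would be plotted.

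**Working it through.** **1. The plan's own figure.** 104 + 20 = 124 and 2 × 124 = 248, as stated. For one coefficient in a linear model with 20 predictors (F test, 1 and 103 df, two-sided 5%), take r² = 0.07, so r = 0.265 and f² = 0.07/0.93 = 0.0753. With noncentrality 0.0753 × 105 = 7.9, power is 0.795. With 0.0753 × 124 = 9.3 it is 0.857. The rule is sound for a linear outcome. Since the plan gives medium no number, r = 0.265 is an assumption: it is the value at which the rule returns .80. The two-sided 5% level is also assumed.

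**2. Event rates.** 15/66 = 22.7% (progression in hospital, the closer analogue) and 49/487 = 10.1% (severity at admission, used only as a low-end case) are background figures. 15% and 20% are assumed points between them.

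**3. Carrying the effect to a 0/1 outcome.** Holding the partial correlation fixed, with independent normal predictors, ln OR per SD = r/√(p(1−p)(1−r²)). At p = 0.227 this is 0.2646/√(0.1756 × 0.93) = 0.655; at p = 0.101 it is 0.911. The large-sample power Φ(b√(Np(1−p)) − 1.96) then does not depend on p, because b√(Np(1−p)) = r√N/√(1−r²). The fall in power at low rates is thus a small-sample effect of few events per predictor, and has to be simulated.

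**4. Simulated power, N = 124, 20 predictors.** Ranges cover up to six designs: independent normal predictors, or a correlated mix of 13 continuous and 7 binary, with or without four other prognostic predictors. They also include separately coded repeats. Seven of the 19 listed predictors are binary: the six in "type of symptoms (cough, fever and dyspnea), comorbidities (presence of diabetes, hypertension, ischemic heart disease" and sex. Prevalences (0.2–0.5) and latent correlation (0.2) are assumptions. The main runs used 800 data sets per cell (simulation SE at most 0.018). For Wald, fits with no finite estimate count as non-detections.

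| Severe | Events in 124 (per predictor) | Events in 248 | ln OR per SD* | Nominal Wald | Firth or size-adjusted |
|---|---|---|---|---|---|
| 22.7% | 28.2 (1.4) | 56.4 | 0.655 | 0.78–0.83 | 0.71–0.79 |
| 20% | 24.8 (1.2) | 49.6 | 0.686 | 0.78–0.83 | 0.73–0.78 |
| 15% | 18.6 (0.9) | 37.2 | 0.768 | 0.65–0.81 | 0.70–0.76 |
| 10.1% | 12.5 (0.6) | 25.0 | 0.911 | 0.29–0.64 | 0.60–0.71 |

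*Independent normal predictors; solved separately in the other designs.

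Nominal Wald rejects about 6–9% under the null, and Firth about 4–5%. Part of the Wald figure at 20–23% is therefore excess size.

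**5. Sensitivity to the meaning of medium.** At r = 0.30, size-adjusted Wald power is 0.87, 0.84, 0.84 and 0.66 at 22.7%, 20%, 15% and 10.1%. If medium is instead a fixed odds ratio (ln OR 0.549 per SD, which is r = 0.265 at a 50:50 outcome), Wald power is 0.61–0.67 at 22.7% and 0.28–0.36 at 10.1%.

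**6. The half-sample histograms.** Data sets of 248 were split at random into halves, with five informative and 15 noise predictors and C about 0.78–0.80 in the main runs. The ratio is the half-sample over the whole-sample coefficient, for the informative predictors. The last column also draws on the designs of step 4.

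| Severe | Ratio, ordinary ML | Ratio, Firth | Full-model half-samples with no finite ML estimate |
|---|---|---|---|
| 22.7% | 1.18–1.22 | 0.98–0.99 | 0–1% |
| 15% | 1.28–1.34 | 0.98–0.99 | 1–14% |
| 10.1% | 1.36–1.50 | 0.95 | roughly 15–30% with independent predictors; up to 55% in correlated designs |

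At 10.1%, 15–30% of 200 splits is 30–60 splits.

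**7. Shift against spread.** Two simulations set the whole-sample estimate against the half-sample histogram. For informative predictors it lay inside the interquartile range in 90%, 85% and 79% of cases at 22.7%, 15% and 10.1% in one, and in about 74–82% in the other. In the first, it was always inside the central 80%, the median offset was about 0.25–0.32 histogram SD, and noise predictors lay inside the interquartile range in 98–100% of cases.

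**8. Where the problem fades.** A correctly chosen five-variable model fitted by ordinary ML had ratios of 1.03–1.07, no inestimable half-samples, and a drop in C of 0.04 at 22.7% and 0.07 at 10.1%. Full-model power in all 248 is 0.97–0.99 at both background rates.

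**The case against.** The plan calls its figure an approximate rule of thumb. At 22.7%, the closer of the two background rates, nominal Wald power is 0.78–0.83 and almost every split can be estimated. The low-end results rest on a rate for severity at admission, and the highest inestimable shares need assumed correlations and four other prognostic predictors. The final coefficients come from all 248 patients. A shift due to overfitting is also something a diagnostic ought to show before the model is reduced.

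Most of this stands, and it limits the point. It does not supply the missing event rate: .80 is approached only under conditions the plan does not state, and at 22.7% a test that holds its size gives 0.71–0.79.

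A reader might infer that the planned stability check would look failed. The documents do not support that. Results analysis sets no numerical criterion, and the shift is modest against the width of the histograms (step 7). A reader might also take 10.1% as the plan's expected rate. It is a background figure for a different quantity.

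**Conclusion.** The point holds as a condition missing from the stated power. The .80 is correct for a linear outcome. For the plan's logistic model it is roughly met by a nominal Wald test at 20–23% severe cases, borderline or short at 15%, and missed at about 10%. Tests that hold their size fall slightly short at 20–23% and clearly short at 10%. These figures assume partial r 0.265, a two-sided 5% test and 20 predictors. A larger r raises them, and a fixed odds ratio lowers them at every rate.

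A second consequence is that unpenalised full-model histograms will sit systematically away from the whole-sample estimates, by about 20% at 22.7% and 35–50% at 10%. Inestimable splits become a practical problem only towards the low end.

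It would be tempting to conclude that 248 is too few or that the final score is undermined. Neither follows: the sums are right, and the reduced model fitted on all 248 is much less affected. The plan should be corrected. Confidence is medium, because the true event rate and the intended effect size are unknown.

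**What to change.** Keep N = 248.

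Replace the .80 with power for the logistic model over a stated event-rate range, naming the effect size, the significance level and one test used throughout. For example: assuming 15–23% severe cases (19–28 in the fitting half of 124, 37–56 in 248), power to detect one predictor with partial correlation 0.265 among 20, by a two-sided 5% Firth penalised likelihood-ratio test, is about 0.70–0.79; at about 10% (12–13 and 25 cases) it is about 0.60–0.71, and .80 is not expected.

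Fit the full 20-predictor models by penalised likelihood, both the 200 half-sample fits and the whole-sample fit they are compared with. Firth with an intercept correction, so that mean predicted risk matches the observed rate, would serve. Every split can then be estimated and the centring comparison is meaningful. The reduced model can stay with ordinary maximum likelihood.

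The cost is one reworded paragraph and one fitting option, with no extra patients. The stated power becomes less favourable, and the coefficients are shrunken and must be read as such. Without the intercept correction, plain Firth inflates predicted risk: on average 25.3% against 22.6% observed, and 14.3% against 10.1%, in simulation. This matters because Primary Analysis computes a probability for every subject. Penalisation does not cure the full model's drop in C, which with Firth is still 0.17 at 22.7% and 0.26 at 10.1%.
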